2.2.1. SSA Primary Estimands

2.2.1.1. Primary RSV Immunogenicity Estimands

The primary estimands for the RSV immunogenicity objective will use the hypothetical strategy and compare the RSVpreF immune response in participants without the intercurrent events. In other words, the immune response is estimated in the hypothetical setting where participants follow the study schedule and protocol requirements as directed. It includes the following 5 attributes:

- **Treatment condition:** Randomized to combination RSVpreF + qIRV or RSVpreF alone.
- **Population**: Adults ≥60 years of age, as defined by the study inclusion and exclusion criteria.
- Variables: RSV serum NTs for subgroup A and subgroup B measured at 1 month after vaccination with combination RSVpreF + qIRV (Visit A102) and at 1 month after RSVpreF alone for the sequential-administration group (Visit A103).
- Intercurrent events: The following intercurrent events could impact the interpretation or the measurement of the immune response:
 - 1. The participant did not receive the study intervention as randomized.
 - 2. The participant did not meet the study inclusion criteria or did meet the exclusion criteria.
 - 3. Major protocol violations: The participant received a prohibited vaccine or treatment that may alter the immune response.
 - 4. Blood was taken outside an acceptable window for immunogenicity evaluation (<27 days or >42 days after RSVpreF alone or combination RSVpreF + qIRV administration).

The clinical question of interest is based on the comparison of the immune response elicited between combination RSVpreF + qIRV with that elicited by RSVpreF alone, without any influence from any other immune-modifying drugs or vaccines and measured within a homogeneous time window. Therefore, all data after intercurrent events 1, 2, and 3, as well as all data at intercurrent event 4, if collected, will be excluded. Major protocol violations will be determined by clinical review (through the data-handling memo).

• Population-level summary: GMR of NT, defined as the ratio of RSV A– and RSV B–neutralizing GMTs between the combination and RSVpreF-alone vaccine groups.

2.2.1.2. Primary HAI Immunogenicity Estimands

The primary estimands for the HAI immunogenicity objective will use the hypothetical strategy and compare the HAI immune response among participants without the intercurrent events. In other words, the immune response is estimated in the hypothetical setting where participants follow the study schedule and protocol requirements as directed. It includes the following 5 attributes:

- Treatment condition: Randomized to combination RSVpreF + qIRV or qIRV alone.
- **Population**: Adults ≥60 years of age, as defined by the study inclusion and exclusion criteria.
- Variables: Strain-specific HAI titers measured at 1 month after vaccination with combination RSVpreF + qIRV (Visit A102) and 1 month after qIRV alone for the sequential-administration group (Visit A102).
- Intercurrent events: The following intercurrent events could impact the interpretation or the measurement of the immune response:
 - 1. The participant did not receive the study intervention as randomized.
 - 2. The participant did not meet the study inclusion criteria or did meet the exclusion criteria.
 - 3. Major protocol violations: The participant received a prohibited vaccine or treatment that may alter the immune response.
 - 4. Blood was taken outside an acceptable window for immunogenicity evaluation (<27 days or >42 days after qIRV alone or combination RSVpreF + qIRV administration).

The clinical question of interest is based on the comparison of the immune response elicited between combination RSVpreF + qIRV with that elicited by qIRV alone, without any influence from any other immune-modifying drugs or vaccines and measured within a homogeneous time window. Therefore, all data after intercurrent events 1, 2, and 3, as well as all data at intercurrent event 4, if collected, will be excluded. Major protocol violations will be determined by clinical review (through the data-handling memo).

• **Population-level summary:** GMR, defined as the ratio of strain-specific HAI GMTs between the combination and qIRV-alone vaccine groups.

2.2.1.3. Primary Safety Estimands

The primary estimands for the safety objective will use the treatment policy strategy and estimate the safety rate regardless of whether an intercurrent event occurs.

DMB02-GSOP-RF02 7.0 Statistical Analysis Plan Template 31-Jan-2022 PFIZER CONFIDENTIAL TMF Doc ID: 98.03 Page 10 of 46

2.2.1.3.1. Reactogenicity Estimands

Reactogenicity estimands have the following 5 attributes:

- Treatment condition: A total of 5 treatments applied for safety estimands: combination RSVpreF + qIRV administered at Visit A101, qIRV administered alone at Visit A101, placebo administered at Visit A102, RSVpreF administered alone at Visit A102, or qIRV administered alone at Visit A101 followed by RSVpreF administered alone at Visit A102 (qIRV/RSVpreF).
- **Population**: Adults ≥60 years of age, as defined by the study inclusion and exclusion criteria.
- Variables: Each prompted item from the e-diary from Days 1 through 7 after vaccination for each treatment (refer to Section 3.1.3.1 and Section 3.1.3.2).
- Intercurrent events: Some of the intercurrent events listed in Section 2.2.1.1 and Section 2.2.1.2 may apply. However, all data collected after the intercurrent event will be included.
- Population-level summary: The rates of reporting each prompted reactogenicity item in the combination RSVpreF + qIRV group, the qIRV group, the placebo group, the RSVpreF group, and the qIRV/RSVpreF group separately (RSVpreF administered 1 month after qIRV).

2.2.1.3.2. AE Estimands

AE estimands have the following 5 attributes:

- Treatment condition: A total of 5 treatments applied for safety estimands: combination RSVpreF + qIRV administered at Visit A101, qIRV administered alone at Visit A101, placebo administered at Visit A102, RSVpreF administered alone at Visit A102, or qIRV administered alone at Visit A101 followed by RSVpreF administered alone at Visit A102 (qIRV/RSVpreF).
- **Population**: Adults ≥60 years of age, as defined by the study inclusion and exclusion criteria.
- **Variables**: AEs reported within 1 month after vaccination (Section 3.1.3.3).
- Intercurrent events: Some of the intercurrent events listed in Section 2.2.1.1 and Section 2.2.1.2 may apply. However, all data collected after the intercurrent event will be included.
- **Population-level summary:** The rates of reporting AEs and SAEs in the combination RSVpreF + qIRV group, the qIRV group, the placebo group, the RSVpreF group, and the qIRV/RSVpreF (RSVpreF administered 1 month after qIRV) group separately.

2.2.1.3.3. SAE Estimands

SAE estimands have the following 5 attributes:

- **Treatment condition:** A total of 2 treatments applied for safety estimands: combination RSVpreF + qIRV administered at Visit A101, and qIRV alone for the sequential-administration group at Visit A101.
- **Population**: Adults ≥60 years of age, as defined by the study inclusion and exclusion criteria.
- **Variables**: SAEs reported throughout the study (Section 3.1.3.4).
- Intercurrent events: Some of the intercurrent events listed in Section 2.2.1.1 and Section 2.2.1.2 may apply. However, all data collected after the intercurrent event will be included.
- Population-level summary: The rates of reporting SAEs in the combination RSVpreF + qIRV group (Group 1) and qIRV alone for the sequential-administration group (Group 2) separately.

2.2.2. SSB Primary Estimands

2.2.2.1. Primary Safety Estimands

The primary estimands for the safety objective of Substudy B will use the treatment policy strategy and estimate the safety rate regardless of whether an intercurrent event occurs.

2.2.2.1.1. Reactogenicity Estimands

Reactogenicity estimands have the following 5 attributes:

- Treatment condition: 2 treatments applied: Combination (RSVpreF + qIRV) 1.0-mL and combination (RSVpreF + qIRV) 0.5-mL at Visit B101.
- **Population**: Adults ≥50 years of age, as defined by the study inclusion and exclusion criteria.
- **Variables:** Each prompted item from the e-diary from Days 1 through 7 after vaccination for each treatment (refer to Section 3.1.3.1 and Section 3.1.3.2).
- Intercurrent events: Some of the intercurrent events listed in Section 2.2.1.1 and Section 2.2.1.2 may apply. However, all data collected after the intercurrent event will be included.
- **Population-level summary:** The rates of reporting each prompted reactogenicity item in the combination (RSVpreF + qIRV) 1.0-mL group for 50-64 years, 65+ years, and 50+ years; and combination (RSVpreF + qIRV) 0.5-mL group for 50-64 years, 65+ years, and 50+ years separately.

2.2.2.1.2. AE Estimands

AE estimands have the following 5 attributes:

- Treatment condition: 2 treatments applied: Combination (RSVpreF + qIRV) 1.0-mL and combination (RSVpreF + qIRV) 0.5-mL at Visit B101.
- **Population**: Adults ≥50 years of age, as defined by the study inclusion and exclusion criteria.
- Variables: AEs reported throughout the study (Section 3.1.3.3).
- Intercurrent events: Some of the intercurrent events listed in Section 2.2.1.1 and Section 2.2.1.2 may apply. However, all data collected after the intercurrent event will be included.
- **Population-level summary**: The rates of reporting AEs and SAEs in the combination RSVpreF + qIRV 1.0-mL group for 50-64 years, 65+ years and 50+ years; and combination (RSVpreF + qIRV) 0.5-mL group for 50-64 years, 65+ years and 50+ years separately.

2.2.2.1.3. SAE Estimands

SAE estimands have the following 5 attributes:

- Treatment condition: 2 treatments applied: Combination (RSVpreF + qIRV) 1.0-mL and combination (RSVpreF + qIRV) 0.5-mL at Visit B101.
- **Population**: Adults ≥50 years of age, as defined by the study inclusion and exclusion criteria.
- Variables: SAEs reported throughout the study (Section 3.1.3.4).
- Intercurrent events: Some of the intercurrent events listed in Section 2.2.1.1 and Section 2.2.1.2 may apply. However, all data collected after the intercurrent event will be included.
- Population-level summary: The rates of reporting SAEs in the combination RSVpreF + qIRV 1.0-mL group for 50-64 years, 65+ years and 50+ years; and combination (RSVpreF + qIRV) 0.5-mL group for 50-64 years, 65+ years and 50+ years separately.

2.2.3. SSB Secondary Estimands

2.2.3.1. SSB Secondary Immunogenicity Estimands

The secondary estimands for the RSV immunogenicity objective of Substudy B will use the hypothetical strategy and compare the RSVpreF immune response in participants without the intercurrent events. In other words, the immune response is estimated in the hypothetical setting where participants follow the study schedule and protocol requirements as directed. It includes the following 5 attributes:

- Treatment condition: 2 treatments applied: Combination (RSVpreF + qIRV) 1.0-mL and combination (RSVpreF + qIRV) 0.5-mL at Visit B101.
- **Population**: Adults ≥50 years of age, as defined by the study inclusion and exclusion criteria.
- Variables: RSV serum NTs and strain-specific HAI titers measured at 1 month after vaccination with combination (RSVpreF + qIRV) 1.0-mL at Visit B102 and 1 month after vaccination with combination (RSVpreF + qIRV) 0.5-mL at Visit B102.
- Intercurrent events: The intercurrent events listed in Section 2.2.1.1 and Section 2.2.1.2 could impact the interpretation or the measurement of the immune response.

The clinical question of interest is based on the comparison of the immune response elicited between combination (RSVpreF + qIRV) 1.0-mL group and 0.5-mL group, without any influence from any other immune-modifying drugs or vaccines and measured within a homogeneous time window. Therefore, all data after intercurrent events 1, 2, and 3, as well as all data at intercurrent event 4, if collected, will be excluded. Major protocol violations will be determined by clinical review (through the data-handling memo).

• Population-level summary: The group means measured as GMTs for each RSV subgroup (A or B) and GMT of HAI titers of each strain, for the combination RSVpreF + qIRV 1.0-mL group for 50-64 years, 65+ years and 50+ years; and combination (RSVpreF + qIRV) 0.5-mL group for 50-64 years, 65+ years and 50+ years separately.

2.2.4. Additional Estimands

Additional estimands, as supplemental analyses to support the primary and secondary immunogenicity objectives, are defined in Table 2. The table below lists the variables and strategies for addressing intercurrent events, which are listed in Section 2.2.1.1 and Section 2.2.1.2, for the immunogenicity objectives. The remaining 3 estimand attributes — treatment condition, population, and population-level summary — are the same for each objective.

DMB02-GSOP-RF02 7.0 Statistical Analysis Plan Template 31-Jan-2022 PFIZER CONFIDENTIAL TMF Doc ID: 98.03 Page 14 of 46

Objective	Variables	Intercurrent Events Handling Strategy
SSA: Primary RSV Immunogenicity	RSV serum NTs for subgroup A and subgroup B measured at 1 month after vaccination with combination RSVpreF + qIRV (Visit A102) and at 1 month after RSVpreF alone for the sequential-administration group (Visit A103).	Treatment policy
SSA: Primary HAI Immunogenicity	Strain-specific HAI titers measured at 1 month after vaccination with combination RSVpreF + qIRV (Visit A102) and 1 month after qIRV alone for the sequential-administration group (Visit A102).	Treatment policy
SSB: Secondary Immunogenicity	RSV serum NTs for subgroup A and subgroup B and strain-specific HAI titers, measured at 1 month after vaccination with (RSVpreF + qIRV) 1.0-mL or with (RSVpreF + qIRV) 0.5-mL (Visit B102).	Treatment policy

2.3. Study Design

2.3.1. Substudy A

This is a Phase 1b, parallel-group, randomized, placebo-controlled, observer-blinded substudy. Approximately 250 healthy adults ≥ 60 years of age will be randomized 1:1 to either:

- Group 1: combination (RSVpreF + qIRV) (Visit A101) followed by placebo (Visit A102) or
- Group 2: sequential administration of qIRV (Visit A101) followed by RSVpreF (Visit A102) administered 1 month apart.

Randomization will be stratified by 3 age groups (60 to 64, 65 to 79, and \geq 80 years) within each study site. There are 3 scheduled study visits each 1 month apart. To assess immunogenicity, blood samples will be collected prior to vaccination at Visit A101 (Day 1) and Visit A102 (Month 1), and at Visit A103 (Month 2).

Local reactions (redness, swelling, and pain at the injection site) and systemic events (fever, headache, fatigue, nausea, vomiting, diarrhea, chills, new or worsened muscle pain, and new or worsened joint pain) occurring within 7 days after each vaccination visit (Visit A101 and Visit A102) will be recorded in an e-diary device or smartphone app.

AEs and SAEs will be collected from the signing of the informed consent through Visit A103.

2.3.2. Substudy B

Substudy B is designed to evaluate the safety, tolerability, and immunogenicity of RSVpreF and a modified RNA vaccine (qIRV) against RSV and influenza when administered as a combined vaccine in a 1.0-mL formulation and a 0.5-mL formulation.

This 2-visit study will be conducted as a Phase 1b, parallel-group, randomized, placebo-controlled, observer-blinded substudy.

Approximately 200 healthy participants (n=100 per group) will be enrolled in Substudy B.

Note: "Enrolled" means a participant's agreement to participate in a clinical study following completion of the informed consent process.

Healthy adults \geq 50 years of age will be randomized 1:1 to either:

- Group 1: combination (RSVpreF + qIRV) 1.0-mL formulation or
- Group 2: combination (RSVpreF + qIRV) 0.5-mL formulation.

Participants will be randomized by age/sex strata. Randomization will be stratified at the study site by 6 age/sex groups so that approximately 100 participants will be 50 through 64 years of age and 100 will be \geq 65 years of age, in addition to having balanced sex distribution between vaccine groups. These groups are as follows:

- Females 50 through 64 years of age
- Females 65 through 79 years of age
- Females ≥ 80 years of age
- Males 50 through 64 years of age
- Males 65 through 79 years of age
- Males ≥ 80 years of age

Blood will be collected prior to vaccination and at the final study visit.

Local reactions and systemic events occurring within 7 days after vaccination will be recorded in an e-diary device or smartphone application.

AEs and SAEs will be collected from the signing of informed consent through study completion.

3. ENDPOINTS AND BASELINE VARIABLES: DEFINITIONS AND CONVENTIONS

3.1. SSA Primary Endpoint(s)

3.1.1. Primary RSV Immunogenicity Endpoints

RSV A– and RSV B–neutralizing antibody titers will be determined on sera collected at all 3 visits. Only the RSV NTs measured at the Month 1 visit in the combination (RSVpreF + qIRV) group, and RSV NTs measured at the Month 2 visit for the sequential-administration group, are relevant to the primary RSV immunogenicity endpoints.

Titers above the LLOQ are considered accurate and their quantitated values will be reported. Refer to Section 5.3.2 for LLOQ details. Titers below the corresponding LLOQ, or denoted as BLQ, will be set to $0.5 \times$ LLOQ for analysis. Missing assay results will not be imputed.

3.1.2. Primary HAI Immunogenicity Endpoints

HAI titers to the influenza strains will be determined on sera collected at the first 2 visits, but only the immunogenicity results for HAI measured in the combination (RSVpreF + qIRV) group, and in the sequential-administration qIRV group at the Month 1 visit, are relevant to the primary HAI immunogenicity endpoints.

Titers above the LLOQ are considered accurate and their quantitated values will be reported. Refer to Section 5.3.2 for LLOQ details. Titers below the corresponding LLOQ, or denoted as BLQ, will be set to $0.5 \times$ LLOQ for analysis. Missing assay results will not be imputed.

3.1.3. Primary Safety Endpoints

In general, e-diary data that are confirmed as errors will not be used for derivation or analysis.

Feedback was received from the FDA on reactogenicity data collection and analysis. Most recently, the FDA stated the concern of missing e-diary entries for reactogenicity events. However, Pfizer sends reminders to sites to follow up on missing e-diary entries, and the reminders are also sent to sites from the vendor. Also, CRF completion guidelines do allow sites to enter e-diary events into the AE CRF. Therefore, Pfizer uses both sources for the reactogenicity data: the e-diary and the AE CRF. Since the AE CRF did not designate a specific page to collect reactogenicity data that were missing in the e-diary, Pfizer has adopted a process of providing a listing of AEs reported within 7 days after vaccination to the clinical team to review/query the AEs, and to finalize the PTs that should be considered reactogenicity before the database lock. For the AEs reported on the same day of vaccination but missing the AE start time, these AEs are defaulted to be considered AEs after vaccination. Then any AEs reported within 7 days after vaccination that match with those flagged PTs, (either "related," or unrelated as assessed by the investigator) will be pooled with reactogenicity data from the e-diary. If the same reactogenicity is reported on the same day from both the e-diary and the AE CRF, the highest grade from the 2 data sources will be used for that specific day.

> DMB02-GSOP-RF02 7.0 Statistical Analysis Plan Template 31-Jan-2022 PFIZER CONFIDENTIAL TMF Doc ID: 98.03 Page 17 of 46

It should be noted that the data collection in the AE CRF is different from that of the e-diary:

- For redness, swelling, and fever, the measured size of redness and swelling at the injection site and temperature are recorded in the e-diary, but not in the AE CRF. Therefore, the maximum grading for the 3 items reported in the e-diary will be based on actual size and the FDA toxicity grading scale, but the maximum grading of the 3 reactogenicity terms from the AE CRF will be based on the grading scale on the CRF page. For the 7 days, only the maximum grading from both sources will be used for the aggregated severity analysis, though the grading algorithm is different between the 2 data sources.
- For pain at the injection site and all other systemic events, the severity grading algorithm for the e-diary data and the AE CRF may not be the same, though Pfizer will choose the highest-severity grade.

If a participant did not have any e-diary data transferred, the AE CRF data will not be used for derivation because the analysis of reactogenicity will be based on e-diary safety population, which is only restricted to participants who have at least 1 day of e-diary data entered. In other words, if a participant did not report any e-diary data, the participant will not be included in the analysis of reactogenicity data.

Safety	Vaccine Group (as Received)				
Endpoints	Combination:	Sequential	qIRV Alone	RSVpreF	Placebo Only
	RSVpreF +	Administration:		Alone	
	qIRV	qIRV/RSVpreF			
Local	Local reactions	Local reactions	Local reactions	Local reactions	Local reactions
reactions	reported within	reported within	reported within	reported within	reported within
within	7 days after	7 days after	7 days after	7 days after	7 days after
7 days after	Vaccination 1	Vaccination 1 or	Vaccination 1	Vaccination 2	Vaccination 2
vaccination	among	after Vaccination 2	among	among	among
	participants who	among participants	participants who	participants who	participants who
	received the	who received qIRV	received qIRV at	received	received placebo
	combination	at Visit A101 with	Visit A101 with	RSVpreF at	only at Visit
	vaccine at	at least 1 day of	at least 1 day of	Visit A102 with	A102 with at
	Visit A101 with	e-diary transferred	e-diary data	at least 1 day of	least 1 day of
	at least 1 day of	following the	transferred	e-diary data	e-diary data
	e-diary data	vaccination and	following the	transferred	transferred
	transferred	received RSVpreF	vaccination.	following the	following the
	following the	at Visit A102 with		vaccination.	vaccination.
	vaccination.	at least 1 day of			
		e-diary data			
		transferred			
		following the			
		vaccination.			

The table below lists safety endpoints that will be derived for each vaccine group.

DMB02-GSOP-RF02 7.0 Statistical Analysis Plan Template 31-Jan-2022 PFIZER CONFIDENTIAL TMF Doc ID: 98.03 Page 18 of 46

Safety	Vaccine Group (as Received)				
Endpoints	Combination: RSVpreF + qIRV	Sequential Administration: qIRV/RSVpreF	qIRV Alone	RSVpreF Alone	Placebo Only
Systemic events within 7 days after vaccination	Systemic events reported within 7 days after Vaccination 1 among participants who received the combination vaccine at Visit A101 with at least 1 day of e-diary data transferred following the vaccination.	Systemic events reported within 7 days after Vaccination 1 or after Vaccination 2 among participants who received qIRV at Visit A101 with at least 1 day of e-diary data transferred following vaccination and received RSVpreF at Visit A102 with at least 1 day of e-diary data transferred following vaccination.	Systemic events reported within 7 days after Vaccination 1 among participants who received qIRV at Visit A101 with at least 1 day of e-diary data transferred following the vaccination.	Systemic events reported within 7 days after Vaccination 2 among participants who received RSVpreF at Visit A102 with at least 1 day of e-diary data transferred following the vaccination.	Systemic events reported within 7 days after Vaccination 2 among participants who received placebo only at Visit A102 with at least 1 day of e-diary data transferred following the vaccination.
AEs within 1 month after vaccination	AEs reported from Vaccination 1 to before Vaccination 2 among participants who received the combination at Visit A101.	AEs reported from Vaccination 1 throughout the study among participants who received qIRV at Visit A101 and RSVpreF at Visit A102.	AEs reported from Vaccination 1 to before Vaccination 2 among participants who received qIRV at Visit A101.	AEs reported from Vaccination 2 through the end of the study among participants who received RSVpreF at Visit A102.	AEs reported from Vaccination 2 through the end of the study among participants who received placebo only at Visit A102.
SAEs throughout the study	SAEs reported from Vaccination 1 throughout the study among participants who received the combination at Visit A101.	SAEs reported from Vaccination 1 throughout the study among participants who received qIRV at Visit A101.	N/A	N/A	N/A

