3.1.3.1.3. Duration of Each Local Reaction

The duration of each local reaction will be calculated in days as the resolution date of reaction - start date of reaction + 1. Resolution of the event is the last day on which the event is recorded in the e-diary (or AE CRF) or the date the event ends if it is unresolved during the participant's e-diary recording period (end date collected on the CRF) or AE stop date, whichever is longer, unless chronicity is established.

If there is no known end date, the duration will be considered unknown and set to "missing." Participants with no reported reaction have no duration.

As there is a second vaccination at Visit A102, the date the reaction ended for Vaccination 1 should not be after the beginning of Vaccination 2. Therefore, if a reaction is ongoing at the time of Vaccination 2, the end date for the reaction after Vaccination 1 would be the date of the day before Vaccination 2, which will be used for the duration computation.

For the vaccine group receiving sequential administration of qIRV/RSVpreF, the duration will be calculated as total days after Vaccination 1 and Vaccination 2.

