3.1.3.3. Adverse Events

Standard algorithms for handling missing AE dates and missing AE severity will be applied as described in the Pfizer vaccine data standard rules.

For any AE reported in the CRF that was considered as reactogenicity (Section 3.1.3) during the clinical review and data-pooling process, this AE record will not be included in any of the derivations included in Section 3.1.3.3 and Section 3.1.3.4. However, if those reactogenicity AEs lead to discontinuation or were serious AEs, they will still be included in AE data.

The following derivations will be included for each participant:

- 1. Any AE reported within 1 month after vaccination: If the AE started on the same day of vaccination, and the AE start time is before the vaccination time, then this AE will not be counted. Otherwise, if the AE start time is missing or after the vaccination time, the AE will be included.
- 2. Any related AE reported within 1 month after vaccination: This is similar to the above except only the related AE is included (but excluding the related reactogenicity reported within 7 days of vaccination [Section 3.1.3]).
- 3. Any immediate AE reported after vaccination (AE start time is within 30 minutes after vaccination): Only those AEs that start on the same day of vaccination, and with nonmissing AE start time that is within 30 minutes of vaccination, will be included.
- 4. Any severe AE reported within 1 month after vaccination.

- 5. Any life-threatening AE reported within 1 month after vaccination.
- 6. Any AE leading to study withdrawal within 1 month after vaccination.
- 7. Any SAE reported within 1 month after vaccination.
- 8. Any AESI within 1 month after vaccination, based on the AE PT.

The following events are considered AESIs:

- Confirmed diagnosis of influenza.
- Confirmed diagnosis of RSV infection.
- Confirmed diagnosis of myocarditis or pericarditis within 4 weeks after Vaccination 1. See Section 3.6.3 for the evaluation of potential myocarditis or pericarditis.

Each of the above will be derived for the data presentation with 5 vaccine groups. Specifically, for the vaccine group receiving sequential administration of qIRV/RSVpreF, the endpoints will be derived after Vaccination 1 and Vaccination 2.

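### Substudy A summarises AEs for the sequential regimen over two months but for the combination over one, with no combination/placebo column to match

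*SAP*

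**What the plan says.** SAP 3.1.3 sets out five safety columns for Substudy A: combination, sequential qIRV/RSVpreF, qIRV alone, RSVpreF alone and placebo only. In the AE row, labelled as covering one month after vaccination, the cells are:

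- Combination: "AEs reported from Vaccination 1 to before Vaccination 2 among participants who received the combination at Visit A101".
- Sequential: "AEs reported from Vaccination 1 throughout the study among participants who received qIRV at Visit A101 and RSVpreF at Visit A102".
- qIRV alone: "AEs reported from Vaccination 1 to before Vaccination 2 among participants who received qIRV at Visit A101".
- Placebo only: "AEs reported from Vaccination 2 through the end of the study among participants who received placebo only at Visit A102".
- RSVpreF alone: the same window as placebo only.

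SAP 3.1.3.3 applies this layout to every AE derivation: "Each of the above will be derived for the data presentation with 5 vaccine groups". The AE estimand in SAP 2.2.1.3.2 lists the same five treatments, with AEs within one month of vaccination as its variable. Its summary opens with "The rates of reporting AEs and SAEs in the combination RSVpreF + qIRV group" and then names the other four groups separately. Neither section has a combination-then-placebo group.

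The SAE row of the same table is built differently. It follows both randomized groups over the whole study, and its combination cell reads "SAEs reported from Vaccination 1 throughout the study among participants who received the combination at Visit A101".

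Protocol 10.9.5 defines the AE estimand as one month after each vaccination, and protocol 10.9.11.3 defines the vaccine groups as the two randomized arms. SAP 2.1 reports no change from the protocol analysis.

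**The concern.** Substudy A randomizes two regimens: combination then placebo, and qIRV then RSVpreF. For AEs, only the second has a regimen-level summary. The only column carrying the combination's name stops before Vaccination 2, and Group 1's second month appears only under placebo.

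The sequential column therefore gives each participant about twice the time in which to report an AE. Anyone who sets it beside the combination column, which is natural in a study of one combined injection against two separate ones, will see fewer AEs with the combination even if the regimens carry the same risk. The reader cannot repair this from the table, because two monthly percentages do not determine the percentage of participants with an AE in either month. At stake is a fair reading of the primary safety objective, which concerns the combination.

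**Working it through.** **The plan's own figures.** The documents give no AE rate and no sample-size figure for AEs in Substudy A. The probabilities in protocol 10.9.11.5 concern geometric mean ratios and do not bear on this point, so there is no AE figure to reproduce. Monthly AE risk is an assumption and is shown over a range.

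**Inputs.**
- Windows: SAP 3.1.3. Visits are 28 to 35 days apart (protocol 10.9.3), so the combination window is about 28 to 35 days and the sequential window about 56 to 70 days (twice each limit).
- Group size: 125 per group, 1:1 (protocol 10.9.6.1).
- Assumed: the same true monthly risk m in both groups and both months, with m = 5%, 10% or 20%; within-person correlation r between months of 0 or 0.5.

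**Formula.** The one-month percentage is m. The two-month percentage is 2m − [m² + r·m(1−m)], which equals 1 − (1−m)² when r = 0.

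- m = 5%: r = 0 gives 0.10 − 0.0025 = 0.0975; r = 0.5 gives 0.10 − (0.0025 + 0.02375) = 0.07375.
- m = 10%: r = 0 gives 0.20 − 0.01 = 0.19; r = 0.5 gives 0.20 − (0.01 + 0.045) = 0.145.
- m = 20%: r = 0 gives 0.40 − 0.04 = 0.36; r = 0.5 gives 0.40 − (0.04 + 0.08) = 0.28.

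| Assumed monthly risk | Combination column | Sequential column, r = 0 | Sequential column, r = 0.5 |
|---|---|---|---|
| 5% | 5% | 9.8% | 7.4% |
| 10% | 10% | 19% | 14.5% |
| 20% | 20% | 36% | 28% |

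**How often the ordering appears.** With 125 per group and independent months, exact binomial calculation puts the sequential column above the combination column in 91%, 97.5% and 99.7% of trials at the three risks. With equal two-month windows the figures are about 46%, 47% and 47%, the rest being ties or the reverse order.

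**Adding a vaccine effect.** Suppose background risk is 10% a month and each regimen adds the same total vaccine-caused risk of 10%. The combination column is expected to read 1 − 0.9 × 0.9 = 19.0%, and the sequential column 1 − 0.9² × 0.9 = 27.1%. In this model the gap closes only if there are no background AEs in the second month.

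**Why the existing columns cannot be combined.** If Group 1 shows 10% in the combination column and 10% under placebo only, its participant-level two-month percentage can lie anywhere from 10% (the same people) to 20% (different people). The table does not say where.

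**After the fix.** With a combination/placebo column over both vaccinations, both regimens have the same expected percentage under equal risk and the expected difference is 0.

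**The case against.** The plan compares less than the table layout might suggest. Substudy A has no hypothesis (SAP 5.1). AEs are reported per group with Clopper-Pearson intervals (SAP 6.1.4.1), and no difference between the combination and sequential AE columns is specified. The between-group AE analysis that is specified, for Tier 1 events, takes its control from another study (SAP 6.5.1). A reader might infer a false-positive rate: at the three risks above, a Miettinen-Nurminen 95% interval would exclude zero in favour of the combination about 30%, 52% and 81% of the time with independent months, or 11%, 19% and 31% with correlation 0.5. The documents do not support calling this an error of the trial, because nobody plans to compute that interval. This objection stands.

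Like-for-like comparisons also exist already. Combination and qIRV alone share the first month, RSVpreF alone and placebo only share the second, and SAEs are matched over the whole study. AE displays are planned by analysis interval and no table shells are included, so the unequal windows may not share a panel. The sequential cell can also be read as two one-month windows joined, which is close to the protocol estimand. These points limit the harm, but they do not give Group 1 the regimen-level AE figure that Group 2 has.

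The sequential column is restricted to participants who received both vaccines. That may offset some of the gap, by an amount the documents do not allow one to calculate.

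It is tempting to extend the point to reactogenicity. There the windows are seven days after each injection, and two active injections producing more reactions than one is a real feature of the sequential regimen, not an artefact of follow-up time. For duration, the SAP says that for the sequential column "the duration will be calculated as total days after Vaccination 1 and Vaccination 2", so two separate 2-day reactions would read as 4 days. Durations per vaccination are nevertheless derived in the single-vaccine columns (SAP 3.1.3.1). These are presentation choices and not errors.

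**Conclusion.** The point holds as one about the AE display. One randomized regimen has a two-month AE summary and the other does not, under a row label of one month. With identical monthly risk between 5% and 20%, the sequential column would read higher by about 5 to 16 percentage points if months are independent, and by about 2 to 8 points with within-person correlation 0.5. The direction rests on there being some background AEs in the second month; the size rests on the assumed rates and correlation, neither of which is in the documents.

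A reader might go further and infer that the AE analysis is invalid, or that the trial will wrongly conclude the combination is safer. The documents do not support that: the analysis is descriptive, matched one-month columns are present and SAEs are unaffected. This is a cheap improvement to a display that could mislead.

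**What to change.** - In the SAP 3.1.3 table, add a Group 1 combination/placebo AE column covering Vaccination 1 through Visit A103, as the counterpart of qIRV/RSVpreF. Carry it into the AE estimand (2.2.1.3.2), the derivations (3.1.3.3) and the AE tables and bar charts (6.1.4).
- Define the new column as the sequential one is defined, in participants who received both of their injections, so that the denominators match.
- Keep the one-month combination column and present it against qIRV alone.
- Relabel the row so that the two-month columns are not described as one month. Reconcile the label with the protocol 10.9.5 estimand, and record the added regimen-level summaries in SAP 2.1.

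The cost is one more column from data already collected. Its downside is that it includes AEs after the saline dose, so the heading should say so. A matching reactogenicity column and a per-vaccination duration in the sequential column are optional.
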